**Abstract**

Title	Functional imaging of T-cell activation with [  F]F-AraG in urothelial carcinoma patients receiving neoadjuvant or patients with cancer receiving standard of care anti-PD-1 or anti-PD-L1
Patient population	
 
1. Patients with localized bladder cancer who are eligible for the UCSF phase 2 clinical trial of neoadjuvant anti-PD-1 or anti-PD-L1 before definitive surgery (NCT02451423) (Cohort 1), and
 
2. Patients with any cancer type who are planned to initiate standard of care (SOC) anti-PD-1 or anti-PD-L1 (Cohort 2).
 

Rationale for Study	
[F]F-AraG is a novel PET imaging agent that has demonstrated selectivity for activated T-cells in preclinical models and T-cell leukemia cell lines. [F]F-AraG has the potential to serve as a noninvasive functional biomarker in the monitoring of T-cell mediated anti-tumor immune response following administration of an immunotherapeutic agent. [F]F-AraG had been administered in six healthy volunteers with no > Grade 1 adverse events, and the biodistribution of [F]F-AraG has been determined in these volunteers on which radiation dosimetry estimated have been based.
 
In this study, [F]F-AraG uptake in the tumor before and after treatment with the anti-PD-1 or anti-PD-L1 antibody will be measured in localized bladder cancer patients receiving neoadjuvant anti-PD-1 or anti-PD-L1 in the context a clinical trial, as well as in patients with any cancer type (locally advanced or metastatic) receiving SOC anti-PD-1 or anti-PD-L1. Clinical response as well as T cell infiltration within the tumor of a pre-treatment biopsy or resection specimen will be correlated with changes in [F]F-AraG uptake. In the neoadjuvant cohort, pathologic response as well as T cell infiltration within the tumor of the surgical specimen will also be correlated with changes in [F]F-AraG uptake. Results from this pilot study will help to guide future clinical trials of [F]F-AraG in the monitoring of anti-tumor immune responses.

Primary Objective	To assess the change in [  F]F-AraG uptake in primary and/or metastatic tumor(s) on whole-body [  F]F-AraG PET/MR imaging associated with neoadjuvant and SOC anti-PD-1 or anti-PD-L1 treatment.

Secondary Objectives	
 
To correlate change in [F]F-AraG uptake within the primary tumor with clinical and pathologic response in patients treated with neoadjuvant anti-PD-1 or anti-PD-L1 (Cohort 1).
 
To assess [F]F-AraG uptake in lymphoid organs before and after anti-PD-1 or anti-PD-L1 (Cohort 1 and 2).
 

Exploratory Objectives	
 
To correlate change in [F]F-AraG uptake within the primary tumor with quantification of tumor-infiltrating T cells in cystectomy specimen (Cohort 1).
 
To correlate change in [F]F-AraG uptake within the primary tumor and/or metastatic tumor(s) with quantification of tumor-infiltrating T cells in a pre-treatment biopsy or resection specimen (Cohort 1 and 2).
 

Study Design	
This is a single-center cross-sectional imaging study in patients with localized bladder cancer undergoing neoadjuvant atezolizumab as part of the companion clinical trial CC# 14524 (NCT02451423; Phase 2 study of atezolizumab in non-metastatic bladder transitional cell carcinoma), and patients with any cancer type (locally advanced or metastatic) receiving standard of care (SOC) anti-PD-1 or anti-PD-L1. For the neoadjuvant cohort, study participants will undergo whole body PET/MR imaging with [F]F-AraG within 7 days of initiating atezolizumab and within 7 days before surgery. For the SOC cohort, study participants will undergo whole body PET/MR imaging with [F]F-AraG within 7 days of initiating Cycle 1 anti-PD-1 or anti-PD-L1, and between Cycle 1 Day 15 (C1D15) and Cycle 2 Day 7 (C2D7) anti-PD-1 or anti-PD-L1 (see Study Schema). A Simon's two-stage design will be utilized.

Number of patients	
A total of 31 patients will be enrolled over an accrual period of approximately 20 months. 12 patients will be enrolled in the neoadjuvant atezolizumab cohort, and approximately 19 patients will be enrolled in the SOC anti-PD-1 or anti-PD-L1 cohort.

Duration of Therapy	
Each patient will undergo two PET/MR imaging scans. The first imaging will be performed within 7 days of starting anti-PD-1 or anti-PD-L1 (baseline). The second imaging will be performed within 7 days before surgery in the neoadjuvant cohort, and between C1D15 and C2D7 anti-PD-1 or anti-PD-L1 in the SOC cohort. A bolus injection of [F]F-AraG will be administered at each imaging time point. Each injection will be followed by up to two whole-body PET/MR scans. Each probe injection plus PET/MR imaging session is estimated to last up to three hours.

Duration of Follow up	
All patients will be followed for 7 days after each [F]F-AraG PET/MR imaging time point for safety assessment.

[figure not shown]
Duration of study	The study is anticipated to reach completion 20 months from the time the study opens to accrual.
Study Drugs	2'-deoxy-2'-[  F]fluoro-9-β-Darabinofuranosylguanine ([  F]F-AraG) is a radiopharmaceutical imaging agent that will be produced under CGMP (Current Good Manufacturing Practice) regulations under the direction of [name] in the Department of Radiology and Biomedical Imaging Radiopharmaceutical Facility at UCSF. A one-time nominal injection dose of ≤5.7mCi for male subjects and ≤4.4mCi for female subjects will be administered at each imaging time point. A simultaneous whole body MRI will be used for attenuation correction and anatomic localization of [  F]F-AraG uptake and SUV calculation.
Safety Assessments	Patients will be evaluated one day and one week via telephone visit after each radiopharmaceutical injection for safety follow-up. All adverse events will be recorded. Due to the noninvasive and non-therapeutic nature of the study, potential risks of the study are anticipated to be low.
Unique Aspects of this Study	To our knowledge, this is the first study to investigate changes in activated T cell localization in the setting of immunotherapy for cancer utilizing functional PET imaging.

**Study Schema:**

[figure not shown]
- ✓ Age ≥18
- ✓ ECOG 0-1
- ✓ Eligible for CC# 14524 or eligible to receive anti-PD-1 or anti-PD-L1 per SOC
- ✓ Measurable disease
- ✓ No prior immunotherapy or known immunodeficiency

★ Whole body [F]F-AraG PET/MRI imaging

**Cohort 1: Neoadjuvant (N=12)**

**Cohort 2: Standard of care (SOC) (N=19)**

**List of Abbreviations**

AE	adverse event
BMP	basic metabolic panel
BUN	blood urea nitrogen
CBC	complete blood cell (count)
CGMP	Current Good Manufacturing Practice
CR	complete response
CRC	Clinical Research Coordinator
CRF	case report form
CT	computerized tomography
CTCEA	Common Terminology Criteria for Adverse Events
CTLA-4	cytotoxic T-lymphocyte-associated protein 4
CTMS	Clinical Trial Management System
dCK	deoxycytidine kinase
dGK	doxyguanosine kinase
DSMC	Data and Safety Monitoring Committee
DSMP	Data and Safety Monitoring Plan
ECOG	Eastern Cooperative Oncology Group
FAC	2-fluoro-d-(arabinofuranosyl)cytosine
F-AraG	2'-deoxy-2'-fluoro-9-β-D-arabinofuranosylguanine
FDA	Food and Drug Administration
FDG	fluorodeoxyglucose
F/U	follow-up
GCP	Good Clinical Practice
HDFCCC	Helen Diller Family Comprehensive Cancer Center
HIPAA	Health Insurance Portability and Accountability Act (HIPAA)
HIV	human immunodeficiency virus
ICF	informed consent form
ICH	International Conference on Harmonization
IND	investigational new drug application
IRB	Institutional Review Board
IHC	Immunohistochemistry
IV	Intravenous
MR	magnetic resonance
MRI	magnetic resonance imaging
NCI	National Cancer Institute

**List of Abbreviations**

PD-1	programmed cell death protein 1
PD-L1	programmed death-ligand 1
PET	positron emission tomography
PK	Pharmacokinetics
PR	partial response
PRC	Protocol Review Committee
RECIST	Response Evaluation Criteria in Solid Tumors
SOC	standard of care
SUV	standardized uptake values
TURBT	transurethral resection of bladder tumor
UA	urinalysis
WBC	white blood cell

## 1 Background and Study Rationale

In recent years, advances in immunotherapy have resulted in remarkable and durable clinical responses in a subset of patients with advanced cancers. However, even among the tumor types that respond – including advanced melanoma and renal cell carcinoma – only 20%-30% of patients benefit from treatment, suggesting intrinsic immune resistance or an insufficient immune response (Restifo N et al., 2016). Furthermore, because immunotherapeutic agents act by inducing cancer-specific immune responses, clinical responses are typically delayed in comparison to conventional cytotoxic agents (Wolchok JD et al., 2009). A significant unmet need in the field is therefore the development of biomarkers to predict which patients are most likely to benefit from immunotherapy.

Molecular imaging of immune activation by positron emission tomography (PET) is a potential noninvasive strategy to monitor immune activation after treatment with immunotherapy. Increased activity of nucleoside salvage pathways has been associated with the proliferation of adaptive and innate immune cells (Fox CJ et al., 2005, Soler C., 2001). In preclinical models of cancer and autoimmunity, the PET probe [F]-2-fluoro-d-(arabinofuranosyl)cytosine ([F]-FAC), which targets the deoxycytidine salvage pathway, was shown to localize to sites of immune activation (Radu CG et al., 2008) and is predominantly accumulated in proliferative CD8+ T cells (Nair-Gill E et al., 2010).

Recently, a radiofluorinated AraG imaging agent, [F]F-AraG (2'-deoxy-2'-fluoro-9-β-D-arabinofuranosylguanine; trade name VisAcT) was synthesized (Namavari M et al., 2010) with a goal of development for human use. F-AraG is a fluorinated purine derivative with selective T-cell toxicity. A water-soluble AraG prodrug, Nelarabine, is FDA approved for the treatment of relapsed T-cell acute lymphoblastic leukemia and T-cell lymphoblastic lymphomas (DeAngelo DJ, 2009). [F]F-AraG preferentially accumulates in murine and human activated T cells than in naive T cells (**Figure 1**). The accumulation of [F]F-AraG in human activated T cells is also significantly higher than other immune cells, including B cells, macrophages, and dendritic cells (unpublished data). Furthermore, endogenously induced anti-tumor immune response in a viral induced rhabdomyosarcoma (MSV) mouse model was correlated with enhanced [F]F-AraG uptake within the tumors (**Figure 2a**). Analysis of isolated tumors showed that tracer preferentially accumulated in activated CD8+ T cells (**Figure 2b**).

[F]F-AraG is a high affinity substrate for deoxyguanosine kinase (dGK) and a low affinity substrate for deoxycytidine kinase (dCK). Both dGK and dCK are over-expressed in activated T cells. Blocking the expression of either dGK or dCK causes reduction in [F]F-AraG accumulation, while over-expression of either dGK or dCK leads to increased accumulation of [F]F-AraG.

The first-in-human study of [F]F-AraG was performed at UCSF in 2015 (Yaghoubi S et al., 2015). [F]F-AraG was administered at a subpharmacologic, tracer microdose consistent with imaging practices in six healthy volunteers (3 males and 3 females). The distribution of the tracer was evaluated over the first 4 hours after injection. A representative whole body PET/MR image in a healthy volunteer is shown in **Figure 3**. The tracer was well tolerated by all patients and there were no > Grade 1 adverse events. The only AE that occurred in more than one volunteer was positive WBC esterase in the urinalysis without urinary symptoms. Normal uptake was seen in the clearance organs: liver, kidneys and bladder. There appeared to be uptake in the thyroid and parotid glands, as well as limited accumulation in the cardiac muscle. In these first-in human studies, no additional drugs were administered to subjects as the biodistribution was determined

for radiation dose estimates. However, in the present study, oral fluid intake and a diuretic (furosemide) will be administered for subjects to allow rapid clearance of the excreted radiotracer from the renal collecting systems and to provide diluted radiotracer within the background of the bladder, and to enable clear evaluation of distribution of the radiopharmaceutical in the walls of the ureters, bladder, and surrounding structures.

[figure not shown]
Given that immunotherapeutic strategies, in particular immune checkpoint antibodies, focus on the generation of T-cell-based antitumor immunity, we hypothesize that uptake of [F]F-AraG within the tumor will correlate with T-cell mediated immune response in cancer patients treated with immune checkpoint blockade. In May 2016, atezolizumab (Tecentriq), an anti-PD-L1 developed by Genentech Inc. was granted FDA approval for the treatment of previously treated locally advanced or metastatic urothelial carcinoma that had progressed during or following platinum-containing chemotherapy or that had progressed within 12 months of neoadjuvant or adjuvant treatment with platinum-containing chemotherapy. This approval was based on results of a single-arm phase 2 study of atezolizumab in 310 patients with locally advanced or metastatic urothelial carcinoma, demonstrating an objective response rate (ORR) of 14.8% overall, and an ORR of 26% in patients classified as PD-L1 positive by immunohistochemistry (Rosenberg JE, 2009). Since then, in April 2017, atezolizumab was also approved in the front-line setting in patients with locally advanced or metastatic urothelial carcinoma who are not eligible for cisplatin-based chemotherapy (Balar AV et al., 2017).

Currently, PD-L1 inhibitors are approved for bladder cancer, non-small cell lung cancer, and Merkel cell skin cancer (Merkel cell carcinoma), and PD-1 inhibitors are approved for melanoma of the skin, non-small cell lung cancer, kidney cancer, bladder cancer, head and neck cancers, and Hodgkin lymphoma. FDA-approved anti-PD-1/L1 medications include:

[figure not shown]
- Pembrolizumab
- Avelumab
- Atezolizumab
- Nivolumab
- Durvalumab

[figure not shown]
In this study, patients with localized bladder cancer eligible for a companion neoadjuvant trial of atezolizumab in non-metastatic bladder transitional cell carcinoma (CC# 14524; NCT02451423), as well as patients with any cancer type (locally advanced or metastatic) planned to receive anti-PD-1 or anti-PD-L1 per SOC will undergo two whole body PET/MR imaging to assess for changes in tracer uptake with PD-L1 blockade. The neoadjuvant cohort in this study provides a unique opportunity to evaluate the correlation of post-treatment intratumoral immune filtration as well as pathologic clinical response with tracer uptake. Results from this study will guide the development of future clinical trials investigating the role of [F]F-AraG in the monitoring of anti-tumor immune responses.

**Figure 1: [F]F-AraG preferentially accumulates in activated T cells than in naive T cells.** (A) Uptake of [F]F-AraG in human and mouse primary T cells post-stimulation. (B) Pan T cells were isolated from spleen and lymph nodes of mice. Untreated cells as well as CD3/CD28 activated T cells (48 hours) were incubated with [F]F-AraG before subcutaneous implantation into the shoulders before PET/CT imaging.

**Figure 2: Visualization of endogenously induced anti-tumor immune response in a viral induced rhabdomyosarcoma (MSV) mouse model with [F]F-AraG PET.** (A) Viral induced rhabdomyosarcoma was implanted in the left hindleg, and P815 mastocytoma (control) was implanted in the right shoulder. PET/CT was performed on day 14 during the peak anti-tumor immune response in the rhabdomyosarcoma model. (B) CD8+, CD4+ and C19+ cells were isolated from rhabdomyosarcoma tumor one hour after probe injection for radioactivity assay.

**Figure 3:** Whole body [ $^{18}\text{F}$ ]F-AraG PET/MR image in a healthy volunteer.

## 2 Objectives and Endpoints of the Study

### 2.1 Objectives

#### 2.1.1 Primary Objective

To assess the change in [ $^{18}\text{F}$ ]F-AraG uptake in primary and/or metastatic tumor(s) on whole-body [ $^{18}\text{F}$ ]F-AraG PET/MR imaging associated with neoadjuvant and SOC anti-PD-1 or anti-PD-L1 treatment.

#### 2.1.2 Secondary Objectives

1. To correlate change in [ $^{18}\text{F}$ ]F-AraG uptake within the primary tumor with clinical and pathologic response in patients treated with neoadjuvant atezolizumab (Cohort 1).
2. To assess [ $^{18}\text{F}$ ]F-AraG uptake in lymphoid organs before and after anti-PD-1 or anti-PD-L1 (Cohort 1 and 2).

### 2.1.3 Exploratory Objectives

1. To correlate change in [ $^{18}\text{F}$ ]F-AraG uptake within the primary tumor with quantification of tumor-infiltrating T cells in cystectomy specimen (Cohort 1).
2. To correlate change in [ $^{18}\text{F}$ ]F-AraG uptake within the primary tumor and/or metastatic tumor(s) with quantification of tumor-infiltrating T cells in a pre-treatment biopsy or resection specimen (Cohort 1 and 2).

## 2.2 Endpoints

### 2.2.1 Primary Endpoint

To describe the change between pre-treatment and post-treatment maximum standardized uptake values ( $\text{SUV}_{\text{max}}$ ) in the primary and/or metastatic tumor(s) on whole-body [ $^{18}\text{F}$ ]F-AraG PET/MR imaging by study cohort.

### 2.2.2 Secondary Endpoints

1. To compare change in  $\text{SUV}_{\text{max}}$  of the primary tumor in patients who achieve pathologic down-staging (e.g. complete pathologic response) or clinical response (measured by RECIST v1.1), and those without pathologic or clinical response at time of surgery in patients receiving neoadjuvant atezolizumab (Cohort 1).
2. To describe the change between pre-treatment and post-treatment  $\text{SUV}_{\text{max}}$  in lymphoid organs (e.g. lymph nodes) on whole-body [ $^{18}\text{F}$ ]F-AraG PET/MR imaging (Cohort 1 and 2).

### 2.2.3 Exploratory Endpoints

1. To correlate change in  $\text{SUV}_{\text{max}}$  of the primary tumor with the number of tumor-infiltrating CD3+ and CD3+CD8+ T cells in the surgical specimen quantified by immunohistochemistry (IHC) and image analysis in patients receiving neoadjuvant atezolizumab (Cohort 1).
2. To correlate change in  $\text{SUV}_{\text{max}}$  of the primary and/or metastatic tumor(s) with the number of tumor-infiltrating CD3+ and CD3+CD8+ T cells in the pre-treatment biopsy or resection specimen quantified by immunohistochemistry (IHC) and image analysis in patients receiving SOC anti-PD-1 or anti-PD-L1 (Cohort 1 and 2).

## 3 Study Design

### 3.1 Characteristics

This is a single-center cross-sectional imaging study in patients with localized bladder cancer undergoing neoadjuvant atezolizumab as part of the companion clinical trial CC# 14524 (NCT02451423; Phase 2 study of atezolizumab in non-metastatic bladder transitional cell

carcinoma), and patients with any cancer type (locally advanced or metastatic) receiving SOC anti-PD-1 or anti-PD-L1. Only anti-PD-1/L1 FDA approved for a given cancer will be used for Cohort 2. For the neoadjuvant cohort, study participants will undergo whole body PET/MR imaging with [F]F-AraG within 7 days of initiating atezolizumab and within 7 days before surgery. For the SOC cohort, study participants will undergo whole body PET/MR imaging with [F]F-AraG within 7 days of initiating Cycle 1 anti-PD-1 or anti-PD-L1 and between Cycle 1 Day 15 and Cycle 2 Day 7 anti-PD-1 or anti-PD-L1.

### 3.2 Number of Subjects

A total of 31 patients will be enrolled over an accrual period of approximately 20 months. Twelve (12) patients will be enrolled in the neoadjuvant atezolizumab cohort, and 19 patients will be enrolled in the SOC anti-PD-1 or anti-PD-L1 cohort.

### 3.3 Eligibility Criteria

Patients must have baseline evaluations performed prior to the first injection of [F]F-AraG and must meet all inclusion and exclusion criteria. In addition, the patient must be thoroughly informed about all aspects of the study, including the study visit schedule and required evaluations and all regulatory requirements for informed consent. The written informed consent must be obtained from the patient prior to enrollment. The following criteria apply to all patients enrolled onto the study unless otherwise specified.

#### 3.3.1 Inclusion Criteria

1. Age  $\geq$ 18 years
2. Histologically or cytologically documented cancer to which anti-PD1 or anti-PDL1 are approved therapies
3. Eligible for with plan to undergo neoadjuvant treatment with atezolizumab followed by surgery as part CC# 14524, or planned to undergo treatment with anti-PD-1 or anti-PD-L1 per standard of care
4. Must have measurable disease by RECIST v1.1 regardless of disease stage (e.g. localized, locally advanced, or metastatic)
5. In female patients, negative pregnancy test with no plans to become pregnant during the duration of the study
6. Able to provide informed consent and follow the study guidelines
7. Archival tumor tissue from biopsy or resection will be required for all patients. Archival tissue should be of good quality based on total and viable tumor contents. Fine-needle aspiration, brushing, and cytologic cell pellets are not acceptable.

#### 3.3.2 Exclusion Criteria

1. History of prior treatment with immune checkpoint antibodies (e.g. anti-PD-1, anti-PD-L1, anti-CTLA-4 antibody) or co-stimulatory agonist antibodies (e.g. anti-41BB, anti-OX40)

- a. Prior intravesical treatment with BCG is allowed. However, the last dose must be at least 6 weeks from time of enrollment and patients must have documented progressive disease at least 6 weeks from completion of last BCG.
2. Diagnosis of immunodeficiency including history of Human Immunodeficiency Virus (HIV)
3. Receiving systemic steroid therapy or any form of immunosuppressive therapy within 7 days prior to first injection of [F]F-AraG.
  - a. Topical and inhaled corticosteroids are allowed.
4. Prior allogeneic stem cell or solid organ transplant
5. Known psychiatric or substance abuse disorders that would interfere with cooperation with the requirements of the study
6. Biopsy or resection of the primary tumor within 14 days the first injection of [F]F-AraG
7. Contraindication to MRI imaging, as determined through review of the UCSF MRI screening form by study investigator (Appendix 4)
  - a. UCSF screening form available online:  
<https://radiology.ucsf.edu/sites/radiology.ucsf.edu/files/wysiwyg/research/brainchange/MRI%20Screening%20Form-BrainChange.pdf>
8. Evidence of active infection within 14 days of study enrollment
9. Female patients who are pregnant or breastfeeding
10. Inability to receive furosemide (Lasix), in the opinion of the treating investigator
11. Patients that plan to receive off-label use of anti-PD1 or anti-PDL1

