### 5.3 Follow Up Procedures

Patients will be evaluated one day and one week by telephone after the radiopharmaceutical injection for safety follow-up. All adverse events will be recorded.

- Cohort 1 (neoadjuvant cohort): Following completion of neoadjuvant atezolizumab cycles per corresponding study protocol, the patient will return for repeat imaging within 7 days of undergoing surgery.
- Cohort 2 (SOC cohort): Between Cycle 1 Day 15 and Cycle 2 Day 7 anti-PD-1 or anti-PD-L1, the patient will return for repeat imaging.

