### 5.4 Prohibited Medications

Patients should receive no systemic therapy for their cancer other than anti-PD-1 or anti-PD-L1 prior to completion of the two planned [F]F-AraG PET scans.

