## **8 Statistical Considerations and Image Analysis**

### **8.1 Image Processing and Analysis**

Trained nuclear medicine physicians and molecular imaging scientists will evaluate the reconstructed PET, PET/MR images using a PET volume computer-assisted reading software package. Volumetric regions of interest will be chosen around tumors based on anatomic (MR) images and activity within the tumor will be expressed in a standardized uptake value (SUV) format where SUV will be defined as [concentration of tracer in tumor]/(injected dose/body weight). Tumor SUV at baseline (before anti-PD-1 or anti-PD-L1 treatment) will be compared with the post-therapy values to determine the change in SUV associated with the therapy. Whole body images will be analyzed to determine differences in tracer distribution relative to pre/post therapy and versus the normal subject pool already studied.

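### The 14-day biopsy exclusion protects only the primary tumour, so a recently biopsied metastasis can supply the baseline SUVmax and hide a true 2-fold rise in Cohort 2

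*Combined protocol and SAP*

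**What the plan says.** - **Section 3.3.2, exclusion 6** bars "Biopsy or resection of the primary tumor within 14 days the first injection of" the tracer. A word is missing after the interval, but on any reading the rule mentions neither metastases nor the second scan.
- **Section 2.2.1** places the primary endpoint "in the primary and/or metastatic tumor(s) on whole-body" imaging. Section 8.2 sizes the trial on the same lesions.
- **Section 3.1** describes Cohort 2, 19 of the 31 patients, as "patients with any cancer type (locally advanced or metastatic) receiving SOC" anti-PD-1 or anti-PD-L1.
- **Section 3.3.1** states: "Archival tumor tissue from biopsy or resection will be required for all patients". It limits neither the site nor the age of that tissue.
- **Section 8.1** states: "Volumetric regions of interest will be chosen around tumors based on anatomic (MR) images". It has no rule for a recently biopsied lesion and none for choosing among several lesions.
- **Section 5.3**, on the second Cohort 2 scan, states: "Between Cycle 1 Day 15 and Cycle 2 Day 7 anti-PD-1 or anti-PD-L1, the patient will return for repeat imaging". No biopsy interval is attached.
- **Section 5.4** restricts only drug treatment between scans: "Patients should receive no systemic therapy for their cancer other than anti-PD-1 or anti-PD-L1 prior to completion of the two planned" scans.

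**The concern.** The exclusion suits Cohort 1, where the disease is localized and the bladder primary is measured. In Cohort 2 the measured lesion may be a metastasis, and the rule as written lets that lesion be biopsied the day before baseline imaging.

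The plan gives no reason for exclusion 6. A limit tied to tracer injection is most naturally read as keeping a procedural reaction out of the uptake measurement. The background section supplies a possible mechanism: "Both dGK and dCK are over-expressed in activated T cells", and these are the kinases for which the tracer is a substrate. SUVmax is set by the hottest point in the region, so a focal reaction could determine it. The same reasoning would apply to a metastasis.

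Baseline SUVmax is the denominator of the response ratio. If it is too high, a patient whose uptake truly doubles is scored as a non-responder. Very few patients decide Cohort 2: none of 8 halts it, and 2 of 19 reject the null hypothesis.

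**Working it through.** **Inputs (section 8.2).** Null doubling rate 1% and alternative 20%. Stage 1 has 8 patients, with a halt at 0 doublings. Stage 2 adds 11, for a total of 19. The null is rejected at 2 or more doublings.

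**Step 1: reproduce the stated design.** The null is not rejected if stage 1 shows no doubling, or if stage 1 shows exactly one and stage 2 none. Hence

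P(reject) = 1 − (1−p)^8 − 8p(1−p)^7 × (1−p)^11.

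- p = 0.20: 1 − 0.1678 − 0.0288 = 0.8034. This reproduces the stated 80% power.
- p = 0.01: 1 − 0.9227 − 0.0668 = 0.0105, inside the stated ceiling of 0.05.
- Chance of a stage 1 halt at p = 0.20: 0.80^8 = 0.1678.

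**Step 2: effect of a raised baseline on one patient's ratio.** The documents give no size, so inflation of 10%, 25% or 50% is assumed, gone by scan 2. If the baseline is multiplied by f, the observed ratio is the true ratio divided by f, and a true rise of 2 × f is needed to score.

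| Baseline inflation | True 2.0-fold rise observed as | True rise needed to score |
|---|---|---|
| 10% | 2/1.10 = 1.82 | 2.2 |
| 25% | 2/1.25 = 1.60 | 2.5 |
| 50% | 2/1.50 = 1.33 | 3.0 |

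**Step 3: effect on Cohort 2.** Let q be the share of true doublings that is masked. The observable alternative becomes 0.20 × (1 − q). The values of q are assumptions.

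| q | Observable rate | Power | Chance of 0 of 8 |
|---|---|---|---|
| 0 | 0.20 | 0.803 | 0.168 |
| 0.10 | 0.18 | 0.755 | 0.204 |
| 0.20 | 0.16 | 0.697 | 0.248 |

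Using unrounded values, power falls by 0.8034 − 0.7551 = 4.8 points or 0.8034 − 0.6966 = 10.7 points. The chance of a stage 1 halt rises by 0.2044 − 0.1678 = 3.7 points or 0.2479 − 0.1678 = 8.0 points.

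**Step 4: biopsy between the scans.** Now the numerator is multiplied by f. For an unchanged lesion the observed ratio is 1.10, 1.25 or 1.50, always below 2. To cross the cut-off the lesion must truly have risen by 2/f: 1.82-fold, 1.60-fold or 1.33-fold.

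**The case against.** The strongest reply is that the route to harm is inferred at each step.

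- **Tissue.** A reader might infer that the tissue requirement forces a fresh biopsy. It does not: section 3.3.1 asks for archival material, and the study calendar schedules no on-study biopsy. A recent biopsy of a metastasis would come from ordinary care, at an unknown frequency. This stands.
- **Mechanism.** The background section reports preferential uptake in activated T cells, and higher uptake there than in B cells, macrophages and dendritic cells. No section shows raised uptake after a biopsy. Exclusion 6 suggests the authors had some such concern, but gives it no size or duration. This stands too.
- **Power figures.** Step 3 assumes complete masking, yet Step 2 shows that sufficiently large rises would still score. The biopsied lesion must also be the one that decides the patient's result, which section 8.1 leaves open. The losses are therefore upper bounds for a given share of patients affected.
- **False doublings.** A reader might infer that a biopsy before scan 2 manufactures responders and inflates the type I error. Step 4 does not support this for an unchanged lesion, and the documents offer no false-doubling rate, so no type I figure is given here.
- **Consequence.** The abstract calls this a pilot, section 2.2.1 words the primary endpoint descriptively, and section 8.4 follows a 0-of-8 result with re-evaluation of the imaging protocol. This softens the cost of a wrong halt but does not remove it.

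None of these replies closes the gap in scope: no other section covers a recently biopsied metastasis at baseline.

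**Conclusion.** The point holds as a mismatch between the exclusion and the endpoint. The 14-day rule protects the primary tumour, while the endpoint may be read from a metastasis, chiefly in Cohort 2. Followed as written, the plan admits a freshly biopsied lesion as the source of baseline SUVmax. If uptake there is raised at baseline and has settled by scan 2, the bias runs against detecting a true doubling.

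The size is unknown. The loss of 4.8 to 10.7 points of power, and the added 3.7 to 8.0 points of stage 1 halt probability, rest on 10% to 20% of true doublings being fully masked. They are not a forecast.

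The between-scan gap exists in both cohorts but is the weaker part. At the inflation assumed, it matters only for lesions that have truly risen by about 1.3- to 1.8-fold. The correction is worth making because it is specific and cheap, not because the design fails without it.

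**What to change.** 1. In sections 3.3.2 and 8.1, apply the plan's existing 14-day interval before the first injection to any lesion, primary or metastatic, that will supply SUVmax. Supply the missing word in exclusion 6 in the same edit.
2. State that a patient with another measurable, unbiopsied lesion stays eligible, and that this lesion is used at both scans.
3. Record the date and site of any biopsy up to scan 2.
4. Keep a patient whose measured lesion is biopsied between the scans in the denominator, flag the case, and report the 2-fold count with and without such patients as a sensitivity analysis. Removing them from the endpoint would be worse: section 3.5 replaces only patients who miss the second scan, so the denominator of 19 would become undefined.

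**Cost.** Short additions to sections 3.3.2 and 8.1, a case report form entry and one sensitivity table. The sample size, decision rule and calculated power of 80.3% do not change. An occasional patient whose only measurable lesion was just biopsied could not enter, or could enter only if the 14 days elapse within the baseline imaging window, which section 3.1 ties to 7 days around the start of treatment. The rule should be fixed before SUV results are reviewed, so that no lesion is dropped after its value is known.
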